We are conducting an epidemiological prostate cancer case-control study in Baltimore, Maryland. Participants will be African-American and Caucasian males who reside in Baltimore city and surrounding areas. The study is ongoing and will recruit 1000 prostate cancer cases and 1000 population-based controls. The cases are recruited at two Baltimore hospitals, the Veterans Affairs Medical Center and the University of Maryland Medical Center. Cases will have pathologically confirmed prostate cancer. The population-based controls are identified through the Maryland Department of Motor Vehicle database, and are frequency-matched by age and race to cases. Enrollment of controls started concurrently with case accrual. The first 12 months of the study constituted a pilot study, during which we evaluated the recruitment procedures. The study involves the administration of a survey and collection of blood from all study subjects. The survey evaluates family cancer history, tobacco use, medication, occupational history, socioeconomic status, and risk factors for prostate cancer. Freshfrozen tumor specimens will be obtained from cancer patients if available. The study is supported by an epidemiological infrastructure that has been developed by our resource contractor at the University of Maryland for a lung cancer case-control study. This lung cancer study is ongoing, and the controls that are recruited for the prostate cancer study are joint controls with the lung cancer study. Hence, population-based male controls recruited by our contractor have double eligibility for the concurrent lung and prostate cancer studies. To achieve an age and race matching of cases and controls in the prostate study, we will over-sample male controls in the lung study.

We will test the primary hypothesis that genes and environmental exposures, including infections and medical history, and interactions between these factors modify prostate cancer susceptibility and contribute to the excessive disease risk among African-American men. As the secondary goal, we will study gene expression profiles of prostate tumors to identify changes in tumor biology that are associated with exposure to genetic and environmental risk factors. It is a focus of this research to identify mechanisms in tumor biology that may cause the aggressive nature of prostate cancer in African-American men.

TABLE OF CONTENTS

1 1.1 1.2	INTRODUCTION STUDY OBJECTIVES BACKGROUND AND RATIONALE	5 7 8

1 INTRODUCTION

Prostate cancer (PCa) is a leading cause of cancer death among men in Western countries (1,2). About 220,000 new cases of PCa were projected for the United States (US) in 2004, and one in six men will develop PCa during his life (1). The disease incidence is still increasing, and disease rates have risen during recent decades in virtually every population-based registry around the world (2). PCa is usually a latent disease, but 25-30% of the tumors behave aggressively, resulting in almost 30,000 deaths among US males per year. Large racial and geographic differences have been observed with a 40-fold difference in incidence between low-risk and high-risk populations. The highest incidence rates were found among African-American men in the US with 137 reported cancers per age-adjusted 100,000 man-years for 1988-1992, versus only 2.3 for men from Shanghai, China (2). Although Caucasians have a significantly lower incidence and mortality rate than African-Americans in the US, the rates are still relatively high when compared with some European countries.

The reasons for the large racial and geographic differences are poorly understood but both environmental and genetic risk factors are thought to be involved. Migrant studies support the involvement of environmental factors (2-4). The adoption of a Western-type diet has been found to strongly increase the risk for PCa (5,6). High meat and animal fat intake, and excessive alcohol consumption, correlate positively with PCa risk (7-9), while a diet that is either high in phytoestrogens (10), such as a soy diet, or in allium vegetables (11) appears to be protective. Although smoking does not appear to be associated with the incidence of PCa (12,13), an association between current smoking and high grade or metastatic PCa has been reported (14-17). It suggests that smoking promotes the progression to a more advanced disease. Other observations point to the role of genetic susceptibility factors in human PCa. The lifetime risk of PCa increases 1.5 to 4-fold in men with one or two first-degree relatives with PCa (18). A Scandinavian study of twins estimated that 42% (95% CI: 29% - 50%) of the observed PCa susceptibility was associated with inherited genetic risk factors (19). Genetic risk factors are particularly significant at a younger age, and the attributable risk of inherited susceptibility is thought to be as high as 30%-40% among men diagnosed with PCa at age 55 years or younger (18). The importance of genetic susceptibility is further suggested by the finding that only humans and dogs, but not other mammals develop PCa (20). Recent reports indicate that PCa biology is different in African-Americans when compared with Caucasians. African-American men develop higher stage carcinomas earlier in life than Caucasian men (21). It appears that both an earlier onset and a more rapid progression of the disease in African-Americans contribute to the difference in mortality between the two ethnic groups (22). Such observations are supported by additional data. The Prostate Cancer Outcomes Study concluded that traditional socioeconomic, clinical, and pathologic factors, could not explain the increased risk of advanced-stage PCa in African-American men (23). Autopsy examination of prostate specimens revealed that the frequency of small latent carcinomas is similar in low-risk and high-risk populations (4,24). In contrast, larger and highergrade carcinomas are more common in high-risk than in low-risk populations, and the frequency correlates with the incidence of clinical PCa. The data show that genetic and/or environmental factors modulate the progression from a small, microscopic carcinoma into a large carcinoma (4,25), and that tumor progression is the critical step that defines the strong ethnic differences in PCa risk and mortality.

NCI IRB Approval:October 28, 2004Protocol Number:05-C-N021

Most prostate tumors are adenocarcinomas. Several benign and malignant lesions have been identified that precede clinical PCa. Focal prostatic glandular atrophy and post-atrophic hyperplasia are potential precursors of prostatic intraepithelial neoplasia (PIN) and adenocarcinoma, and they occur in close association with chronic inflammation (26,27). PIN is physically and temporally associated with concurrent malignancies. It frequently arises in inflamed areas (28). Many consider PIN as the most likely precursor of invasive adenocarcinoma. Acute and chronic inflammation is commonly observed in prostate biopsies (29) and causes atrophic acini and hyperplasia. It has been proposed that the inflammation-to-carcinoma sequence is of great importance in prostate carcinogenesis (28,30). The finding that two food supplements with antioxidant properties, selenium and vitamin E, protect against PCa (31,32) supports this notion.

Endogenous Mediators of Prostate Cancer Progression

Androgens are essential for the growth of the prostate gland, and are believed to be significant in the etiology of PCa (33). Large doses of androgen can induce PCa in rodents, and eunuchs rarely develop PCa. Androgen ablation, or anti-androgen therapy, frequently causes the regression of prostate tumors, at least temporarily (34). Men with serum testosterone in the upper quartile of the population have an approximately two-fold higher risk for developing PCa, as indicated by a meta-analysis after adjusting for age and body mass index (35). However, many studies that examined the relationship between circulating sex hormones and PCa risk failed to show an association (33). It is possible that blood hormone concentrations may not reflect intraprostatic androgen activity.

Non-androgenic mediators of prostatic growth have been described. A high blood concentration of insulin-like growth factor-1 (IGF-1) has been associated with an increased risk of advanced PCa (36-39). Insulin resistance, and chronically high insulin blood concentrations, are also predictors of increased cancer risk (40,41). The increased secretion of IGF-1 and insulin appears to be linked to a Western-style diet, a known risk factor for PCa. Other data suggest that several endothelial-derived factors and mediators of inflammation, such as interleukin-6 and -8, endothelin-1, vascular endothelial growth factor (VEGF), eicosanoids and nitric oxide, contribute to PCa progression (42-48). Mediators of inflammation, such as eicosanoids and nitric oxide, have also proangiogenic properties and induce functional changes in the vasculature that will lead to vessel remodeling, stimulation of endothelial cell mitosis and vessel growth. Overexpression of cyclooxygenase-2 and nitric oxide synthase-2 in human PCa has been reported (48-51). Chronic inflammation of the prostate may, therefore, promote cancer progression through the angiogenesis pathway.

NCI IRB Approval: Protocol Number: October 28, 2004 05-C-N021

1.1 STUDY OBJECTIVES

PRIMARY OBJECTIVE

We will examine the association of allele variant genes with PCa risk. The key aim is to examine pathways in relation to PCa, e.g., host defense, inflammation pathways. Within cases, we will examine the relation of genetic variants to molecular, clinical, and prognostic endpoints. The objective will be accomplished with 1) genotype analysis of blood DNA from 1000 cases and 1000 controls and 2) collection of data from questionnaires, medical and pathology records, and the National Death Index. We are testing the hypothesis that susceptibility to nonhereditary PCa is modified by allele variant genes that modulate host defense, inflammation, hormone-stimulated survival and proliferation of mutant cells, the DNA repair capacity, or tumor angiogenesis. The susceptibility may vary by race and lifestyle (gene-environment interaction).

SECONDARY OBJECTIVES

- We will develop gene expression profiles of 60-100 tumors, and will compare gene expression in low-stage and high-stage tumors of African-Americans with gene expression in same stage tumors of Caucasians. The objective is to find gene expression profiles of cancerous and non-cancerous prostate tissue that are characteristic for the disease in African-American men. *We are testing the hypothesis that the molecular signature of primary prostate tumors is different between African-American and Caucasian men. The gene expression profile of African-Americans is associated with an early onset of the disease, a more rapid cancer progression and poor outcome.*
- We will examine the gene expression profiles of tumors from current (n = 10-15) and never smokers (n =10-15). We are testing the hypothesis that current smoking induces a gene signature of tumor progression that reveals the mechanism by which tobacco smoke promotes prostate cancer progression.
- We will determine IGF-1 serum concentrations in our study population and compare gene expression profiles of about 10-15 low-stage tumors from patients with blood IGF-1 levels in the extreme quartiles, respectively. We are testing the hypothesis that a high IGF-1 blood concentration modulates gene expression in primary tumors. The molecular profile is associated with disease progression and poor outcome.
- We will correlate IGF-1 serum concentrations with tissue markers such as phoshorylated Akt, reduced apoptosis, increased VEGF expression, and with the phosphorylation of genes that are regulated by Akt. *We are testing the hypothesis that IGF-1 promotes cancer progression by activating the Akt/protein kinase B pathway in the prostate.*

NCI IRB Approval:	October 28, 2004
Protocol Number:	05-C-N021

• We will compare gene expression profiles of about 10-15 low-stage tumors from patients with a vegetable consumption (tomato, allium) in the extreme quartiles, respectively. The dietary intake of these vegetables is assessed by our questionnaire. *We are testing the hypothesis that a diet high in these vegetables modulates gene expression in primary tumors. The molecular profile correlates with good outcome.*

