wild-type genotype (major allele), or the lowest exposure subgroup, as the reference group. Odds ratios and 95% confidence intervals will be calculated by unconditional logistic regression. Regression analysis will be performed in univariate and multivariate models to assess associations between risk factors and cancer susceptibility, and to adjust for possible confounding factors. Case-case analyses, correlating tissue marker expression with tumor staging, hormone blood concentrations, diet or genotypes, will be done by ANOVA, with the student's t-test, or a nonparametric test, such as the Mann-Whitney U rank sum test. To look at trends, the Mantel-Haenszel test for trend will be used to assess the correlation between marker expression/frequency and categorized (e.g., low, medium, high) variables, such as tumor stage, intake of a dietary factor, or IGF-1 blood concentrations. The association between a genotype and outcome will be studied either in a logistic regression model after categorizing into a good and poor outcome group or with the Kaplan-Meier method and the log-rank test. All analyses will be performed with the STATA and SAS statistical software packages.

ANALYSIS OF GENE EXPRESSION PROFILES

The data from the Affymetrix HG-U133A array will be estimated using the RMA procedure from Bioconductor (www.bioconductor.org). Previous analysis on raw data from replicate samples with RMA indicates that the mean standard deviation of log2 intensities is 0.1 across all intensity levels. This corresponds to a typical technical error of 5%-10% (94).

The factorial study design suggests an analysis of variance. We will first examine the four groups for heterogeneity of variances by comparing the ratios of variances between groups to the F-distribution. If the distributions conform, we will follow standard ANOVA procedure. If there is significant departure from agreement, we will perform non-parametric ANOVA using the rank F-test and use the Welch t-test for two group comparisons. We will select differentially expressed genes for contrasts between racial groups at each level of tumor, and for the difference between tumor stages across racial groups. To address the multiple comparisons problem we will use a modified FDR procedure of Benjamini and Hochberg adapted to correlated data (95).

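### The smoking expression contrast in section 1.1 has no stage condition, unlike the race, IGF-1 and vegetable contrasts, so a stage or grade imbalance may be mistaken for a smoking-induced progression signature

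*Protocol*

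**What the plan says.** Four secondary objectives in Protocol section 1.1 compare expression profiles between groups of patients.

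- **Race:** the plan is to "compare gene expression in low-stage and high-stage tumors of African-Americans with gene expression in same stage tumors of Caucasians".
- **IGF-1:** the plan is to "compare gene expression profiles of about 10-15 low-stage tumors from patients with blood IGF-1 levels in the extreme quartiles, respectively".
- **Vegetables:** "We will compare gene expression profiles of about 10-15 low-stage tumors from patients with a vegetable consumption (tomato, allium) in the extreme quartiles, respectively".
- **Smoking:** "We will examine the gene expression profiles of tumors from current (n = 10-15) and never smokers (n =10-15" in the second group as well. The hypothesis is that "current smoking induces a gene signature of tumor progression that reveals the mechanism by which tobacco smoke promotes prostate cancer progression".

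The first three state a stage condition; the smoking objective does not. The Introduction notes that "an association between current smoking and high grade or metastatic PCa has been reported" and takes this to mean that smoking promotes progression. Section 1.2.4 aims to find profiles that separate high from low pathological stage in the same set of 60-100 tumors. Table 6 stratifies those tumors by race and stage, not by smoking.

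For the expression data, section 5.4.3 says "We will select differentially expressed genes for contrasts between racial groups at each level of tumor" and adds stage differences across racial groups. The adjustment for confounders in that section concerns regressions on cancer susceptibility, not expression.

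**The concern.** The protocol supplies both links of a confounding path: smoking with advanced or high-grade disease, and stage with expression. If current smokers' tumors are on average of higher stage or grade, genes that track stage will differ between smokers and never smokers even when smoking changes nothing in a tumor of given stage.

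The false signal also looks like the hypothesis. A stage signature is a progression signature, so a positive result would fit both explanations. FDR control does not protect against this, because the group difference is real and only its attribution is wrong.

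At stake is the mechanistic reading of one secondary objective. Section 5.4.1 lists the association of exposures with expression profiles among the primary objectives, so the contrast is not peripheral.

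**Working it through.** **1. Stage conditions side by side (section 1.1).** Race: same stage. IGF-1: low stage. Vegetables: low stage. Smoking: none stated. No other section matches, stratifies or adjusts the smoking contrast for stage or grade.

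**2. The protocol's own figure.** Table 5 lists 37 tumors at Stage I + II, 11 at Stage III and 1 at Stage IV. Advanced share = (11 + 1)/49 = 24.5%, which agrees with section 1.2.4.

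**3. Expected shift without any smoking effect.**

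shift = (advanced share in current smokers − advanced share in never smokers) × stage effect in log2

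The documents give no stage split by smoking, so these inputs are assumptions: 24.5% advanced in never smokers, a two-fold stage effect (1 log2), and an odds ratio (OR) of 1.5, 2 or 3 for advanced stage in current smokers. The baseline odds are 12/37 = 0.324, and the share in current smokers is OR × 0.324/(1 + OR × 0.324).

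| OR | Advanced share, current smokers | Difference from 0.245 = shift (log2) | Advanced of 15, current vs never |
|---|---|---|---|
| 1.5 | 0.327 | 0.082 | 4.9 vs 3.7 |
| 2 | 0.393 | 0.149 | 5.9 vs 3.7 |
| 3 | 0.493 | 0.248 | 7.4 vs 3.7 |

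**4. How often a single stage gene would be called.** Inputs from section 5.4.1: 13 tumors per group, variance 0.5, significance level 0.001. The standard error of the difference is √(0.5 × 2/13) = 0.277. With the shifts above, a two-sided t-test with 24 degrees of freedom calls such a gene with probability 0.0014, 0.0026 or 0.0064, against 0.001 with no imbalance. Simulating the stage mix within groups, which adds variance, gives slightly lower rates: 0.0014, 0.0021 and 0.0051.

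**5. Wider assumptions.** With advanced shares of 35-50% against 15%, and stage effects of two- to four-fold (1 to 2 log2), the shift is 0.20 to 0.70 log2. The simulated rate at 13 per group is then 0.0035 to 0.038.

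**6. After the fix.** With equal stage mix in the two smoking groups the bias term is zero. The simulated rate returns to nominal: 0.0007-0.0012 at level 0.001.

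**7. Room for imbalance and for restriction.** Table 6 plans 20-40 high-stage tumors among 60-100: 20/60 = 33% at the lower ends and 40/100 = 40% at the upper. That leaves 40-60 low-stage tumors, from which a pT2-only contrast would need 20-30 current and never smokers. The smoking distribution is not given, so feasibility cannot be confirmed.

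**The case against.** **Silence is not a rule.** The protocol does not say that tumors of any stage will be used, and matching or covariates may be set out in an analysis plan that is not shown. The absence of smoking from the ANOVA in 5.4.3 proves little, since the IGF-1 and vegetable contrasts are absent too. That is fair. But which tumors enter a contrast is a matter of specimen selection. Section 1.1 fixes it for the other three contrasts, and with 10-15 per group a badly balanced set is hard to repair later by modelling.

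**Stage may lie downstream of smoking.** On the protocol's own reading smoking promotes progression, so conditioning on stage removes part of the effect under test. This stands as a reason not to rely on the conditioned contrast alone. It does not rescue the unconditioned one, which cannot tell that effect from a plain stage signature. The Introduction also links IGF-1 to advanced disease and section 1.1 ties it to progression, yet the protocol limits the IGF-1 contrast to low stage.

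**The cited evidence fits imperfectly.** It concerns high-grade or metastatic disease. Grade is not pathological stage, and the specimens come from prostatectomy, where Table 5 has 1 of 49 at Stage IV. This stands: the link within the surgical group may be weaker, and a remedy limited to pT stage would leave a grade imbalance untouched.

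**There are downstream checks.** The stage profile is derived separately, so overlap with smoking genes could be inspected, and candidate progression markers go to quantitative PCR. PCR can confirm that a gene differs, but not why. The overlap check is useful but is not planned.

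**Conclusion.** The point holds as a gap in design. Among the between-group expression comparisons in the secondary objectives, only the smoking contrast lacks a same-stage or low-stage condition, and the protocol itself gives the reasons why stage and grade matter there. A positive result may be mistaken for a signature induced by smoking.

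The size is unknown. Under the assumed odds ratios of 1.5 to 3 on a 24.5% base, a gene with a two-fold stage effect shifts by 0.08-0.25 log2. At 13 per group, variance 0.5 and level 0.001, most such genes would not be called. Larger imbalances or stage effects would raise the rate.

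A reader might infer three stronger things that the documents do not support:

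- That a stage signature is bound to be misread as a smoking effect. This depends on an imbalance the protocol does not quantify.
- That current smokers in this study have more advanced tumors. The protocol reports an association from the literature, not from its own patients.
- That the objective cannot be answered at all. It cannot be answered from this contrast without restriction, balancing or adjustment.

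**What to change.** In section 1.1, state how the smoking groups are formed, and in section 5.4.3, how they are analysed, by one of two routes:

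- **Selection:** choose current and never smokers balanced on pathological stage (or within pT2 if numbers allow), Gleason group and race.
- **Modelling:** fit smoking with stage and race as factors, adding Gleason group where numbers allow.

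Under either route, report the stage-conditioned contrast alongside the unadjusted one. Base any claim that smoking induces a progression signature on genes that persist after conditioning.

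The text change is short; the cost lies in the specimens. Modelling spends a few degrees of freedom. Restriction to pT2 gives up the high-stage specimens, 33-40% of the Table 6 plan, and may not be feasible once former smokers are left out and race is balanced; the modelling route is then the fallback. The conditioned contrast also omits any smoking effect that acts through stage, which is why both should be reported.

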1.2 BACKGROUND AND RATIONALE

1.2.1 RATIONALE FOR CONDUCTING THE STUDY IN THE GREATER BALTIMORE AREA

Our goal is to identify and compare genetic risk factors in two ethnic groups, African-Americans and Caucasians. The two hospitals that we chose to recruit PCa patients are located in Baltimore City, Maryland. Baltimore has a large African-American population, and we estimate that about half of the PCa patients at the two hospitals will be of African-American descent. The study will be supported by an existing epidemiologic infrastructure with our contractor at the University of Maryland and an established relationship between our group and the Departments of Pathology at the two hospitals. The Laboratory of Human Carcinogenesis is currently conducting a lung cancer case-control study at the same hospitals and is recruiting population-based controls to match the cases. The controls recruited for the lung study meet the eligibility criteria of the proposed PCa study. The mean and median age of male cases in the lung cancer study is 65-66 years. If the age distribution of the PCa patients does not change in the next 5 years, we expect about the same mean and median age for the PCa cases, as indicated by hospital records and cancer registry data (Tables 1 and 2). Such an age distribution will allow the matching of PCa cases with population-based controls using the established resources. The recruitment will be accomplished by over-sampling of male controls under the current protocol for the lung study. PCa cases will be identified primarily by PSA screening. Needle biopsies are taken to confirm the presence of cancer in screen-positive patients. We expect to recruit up to 25 patients per year, who present with cancer in a needle biopsy and undergo a radical prostatectomy prior to chemotherapy, radiation, or hormone therapy. The remaining patients will have chemotherapy, radiation, or hormone therapy, where only blood samples but no tumor specimens will be collected.

Calendar Year 2001		
Age (yrs) Number of Patien		
40-49	10	
50-59	67	
60-69	126	
70-79	93	
80+	17	
Total	313	

Table 1: Age	Distribution (of PCa Patients	s at the Two	Participating	Hospitals
10010 11150	Distribution	of I Cu I unont	jui ille 1 mo	i untroiputing	inoppituito

	University of Maryland Medical Center Calendar Year 2001			
Age (yrs)	African-American	Caucasian	Total	
40-49	2	5	7	
50-59	21	27	48	
60-69	22	42	64	
70-79	18	19	37	
80+	2	2	4	
Total	65	95	160	

Table 2: Age Distribution by Race/Ethnic Background

